## 11.6.2.2.2 Cotinine

Cotinine will be measured together with nicotine at all the corresponding time points. However, only the data from the three following time points: prior T0, T0 +12 h, T0 + 24 h will be summarized.

The cotinine plasma concentrations will be summarized in a similar manner to the nicotine PK parameters (see Section 11.6.2.1 “Pharmacokinetics”), but will also be split out by sample time point.

Cotinine levels will also be summarized by race as described in Section 11.1.1 “Stratified Presentation”.

TFL number	Title
TABLES	
15.2.4.18	Descriptive Statistics of Plasma Cotinine Concentrations (ng/mL) – PK Population
15.2.4.18.1	Descriptive Statistics of Plasma Cotinine Concentrations (ng/mL) by Sex – PK Population
15.2.4.18.2	Descriptive Statistics of Plasma Cotinine Concentrations (ng/mL) by Nicotine Level – PK Population
15.2.4.18.3	Descriptive Statistics of Plasma Cotinine Concentrations (ng/mL) by Race – PK Population
FIGURES	
15.1.2.12.1	Cotinine Plasma Concentrations (ng/mL) Profiles Geometric Mean ( $\pm$ 95% CI) – Group-1 PK Population
15.1.2.12.2	Cotinine Plasma Concentrations (ng/mL) Profiles Geometric Mean ( $\pm$ 95% CI) – Group-2 PK Population
LISTINGS	
15.3.3.6	Listing of Plasma Cotinine Concentrations (ng/mL) and Sampling Times

## 11.6.2.3 Questionnaires

## 11.6.2.3.1 Urge-to-Smoke Questionnaire of Smoking Urges Brief

The total score and the two factors from the QSU-brief will be listed for all scheduled time points and summarized overall and by the two stratification factors (sex, mCC nicotine level at Admission) for the PK populations, as specified in Section 11.1.1 “Stratified Presentation”. The individual responses to all questions will be listed by product, study day, and assessment time points.

In addition line graphs will be produced for the total score and factors means (and 95% CI) over all timepoints.

The analysis of the subjective effects of smoking (the total score, and Factor-1 and Factor-2 from the QSU-brief) will be performed using the same mixed effects ANOVA adopted for the analysis of CO breath test described in Section 11.6.2.2.1 "Exhaled CO and COHb".

A sensitivity analysis using bootstrap techniques, will also be conducted on the total and factors score of QSU-brief, as described in Section 11.6.3 "Supportive/Sensitivity Analysis".

The main comparison will be the mean difference over all timepoints. LS means for each product, the overall mean difference (THS 2.2 Menthol - mCC or THS 2.2 Menthol - NNS as appropriate) and the mean differences at each time point will be presented in the tables as a point and interval (95% CI) estimate. Figures of the LS mean difference and 95% CI at each time point will be produced.

The data will be presented in the below outputs:

TFL number	Title
TABLES	
15.2.4.12	Analysis of QSU-brief Questionnaire Factors and Total Score – PK Population
15.2.4.14	Descriptive Statistics of QSU-brief Questionnaire Factors and Total Score – PK Population
15.2.4.14.1	Descriptive Statistics of QSU-brief Questionnaire Factors and Total Score by Sex – PK Population
15.2.4.14.2	Descriptive Statistics of QSU-brief Questionnaire Factors and Total Score by Nicotine Level – PK Population
FIGURES	
15.1.2.10.1	QSU-brief Factors and Total Score Profiles Arithmetic Mean ( $\pm$ 95% CI) – Group-1 PK Population
15.1.2.10.2	QSU-brief Factors and Total Score Profiles Arithmetic Mean ( $\pm$ 95% CI) – Group-2 PK Population
15.1.2.11.1	QSU-brief Factors and Total Score Profiles Arithmetic Least Squares Mean Differences ( $\pm$ 95% CI) – Group-1 PK Population
15.1.2.11.2	QSU-brief Factors and Total Score Profiles Arithmetic Least Squares Mean Differences ( $\pm$ 95% CI) – Group-2 PK Population
LISTINGS	
15.3.6.11	Listing of QSU-brief Questionnaire Results

#### 11.6.2.3.2 Modified Cigarette Evaluation Questionnaire

The MCEQ domain scores composed of the three multi-item subscales and two single items from the MCEQ will be listed and summarized overall and by the two stratification

factors (sex, mCC nicotine level at Admission) for the PK populations, as specified in Section 11.1.1 "Stratified Presentation". The individual responses to all questions will be listed.

A mixed effects ANOVA model will be used to estimate mean THS 2.2 Menthol -mCC differences of the MCEQ domain scores and variances, with a REML method, using heterogeneous compound symmetry covariance structure (**Brown and Prescott, 1999**). Subjects within sequence will be used as random effects and fixed effects are period, sequence, and product exposure.

```
Proc mixed data=_data_ method=reml maxiter=200;
  Class subject sequence product period;
  Model response = sequence period product;
  Random subject(sequence) / subject=subject type=csh;
  Lsmean product / pdiff =control('mCC/NNS') alpha=0.05 cl;
  Run;
```

In case of model convergence issues, additional covariance structures will be investigated with the following order: heterogeneous autoregressive(type=arh), variance component (type=vc), and unstructured (type=un).

LS means for each product and the overall point and 95% interval estimate of the difference (THS 2.2 Menthol - mCC) will be presented in the tables.

A sensitivity analysis using bootstrap techniques, will also be conducted on the MCEQ domain scores, as described in Section 11.6.3 "Supportive/Sensitivity Analysis". The data will be presented in the below outputs:

TFL number	Title
TABLES	
15.2.4.15	Analysis of MCEQ Subscales – PK Population
15.2.4.17	Descriptive Statistics of MCEQ Subscales – PK Population
15.2.4.17.1	Descriptive Statistics of MCEQ Subscales by Sex – PK Population
15.2.4.17.2	Descriptive Statistics of MCEQ Subscales by Nicotine Level – PK Population
LISTINGS	
15.3.6.12	Listing of MCEQ Questionnaire Results

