12.5.3 Descriptive Analysis

Primary endpoints will be summarized as described in Section 12.1.3.

An analysis of variance (ANOVA) will be conducted on $AUC_{(0-\text{last})}$ and C_{\max} endpoints in the natural logarithmic scale. The model will include terms for sequence, subjects within sequence, period, and exposure group as fixed effect factors. The results of this analysis for each of $AUC_{(0-\text{last})}$ and C_{\max} are presented in terms of adjusted geometric least square means and 95% confidence intervals for the THS 2.2 Menthol:mCC and THS 2.2 Menthol:NNS ratios.

This approach is consistent with the guidelines in the European Medicines Agency's guidelines for bioequivalence investigations (EMA, 2008) and FDA's Center for Drug Evaluation and Research (FDA, 2001). Carry-over effect will not be tested, as it cannot be statistically distinguished from the interaction between treatment and period in a 2x2 crossover design (ICH E9, 1998).

A sensitivity analysis will be conducted should there be 20% or more missing PK parameter values by repeating the above analyses using mixed effects ANOVA model in the natural log scale with a restricted maximum likelihood method to estimate mean differences and variances as suggested by FDA (FDA, 2001). Subjects within sequence will be used as random effects and fixed effects are period, sequence, and product exposure. To evaluate the sensitivity to the distributional assumptions, point and interval estimates will also be

Confidentiality Statement: Data and information contained in this document are considered to constitute trade secrets and confidential commercial information, and the legal protections provided to such trade secrets and confidential information are hereby claimed under the applicable provisions of United States law. No part of this document may be publicly disclosed without the written consent of Philip Morris International.

estimated by means of the percentile bootstrap technique, which uses 2000 bootstrap samples to preserve the number of subjects per sequence.

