### 11.6.3 Supportive/Sensitivity Analysis

To support the interpretation of the PK analysis, the values of nicotine concentration greater than BLOQ before  $T_0$  will be listed together with any PK parameters excluded from the analysis. Listing will be presented by PK parameter impact, sequence, period and study date.

To better understand the impact of the higher than expected  $T_0$  values, an analysis of the PK parameters will be performed as described above, however the data for subjects with

their  $T_0$  value  $>5\%$  of their  $C_{max}$  value will be excluded from the analysis. Sensitivity analysis will be conducted on the  $C_{max}$  and  $AUC_{(0-last)}$  endpoints for the Group-1 and Group-2 PK populations should there be 20% or more missing PK parameter values. This analysis is conducted on all the available PK parameters and subjects will be excluded from the analysis if the nicotine concentration  $T_0$  value is  $>5\%$  of their  $C_{max}$  value. The analysis will be conducted in the natural log scale using the same mixed effects ANOVA model described in Section 11.6.2.3.2 “Modified Cigarette Evaluation Questionnaire”. Point and 95% interval estimates of the ratios will be back-transformed by exponentiation and tabulated.

The same sensitivity analysis for  $C_{max}$  and  $AUC_{(0-last)}$  endpoints will be conducted on  $t_{max}$ , in both Group-1 and Group-2 PK populations, supporting with THS 2.2 effect estimates on  $t_{max}$  adjusted for period, sequence, and subject within sequence.

In case any time information is imputed for the computation of PK parameters as described in Section 11.1.5 “Handling of Dropouts or Missing Data (including outside the limits of quantification)” in any PK population, the median  $t_{max}$  for THS 2.2 will be calculated following the imputation of missing time data by 0 sec and 30 sec. If the difference between the two median  $t_{max}$  is larger than 5%, a supportive analysis will be conducted by repeating the analyses described in Section 11.6.1 “Primary Analyses” and 11.6.2 “Secondary Analyses” on the  $t_{max}$ ,  $AUC_{(0-last)}$ , and  $AUC_{(0-t)}$  endpoints estimated by means of the imputation of missing time by 0 sec.

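### SAP 11.6.2.3.2 puts heterogeneous compound symmetry on a single random subject effect; if that fit is accepted, the MCEQ and supportive PK intervals are too narrow, while the primary analysis is unaffected

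*SAP*

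**What the plan says.** **Protocol.** Section 12.5.3 describes the mixed-model sensitivity analysis of the primary endpoints: "Subjects within sequence will be used as random effects and fixed effects are period, sequence, and product exposure". It names no heterogeneous structure. Section 12.6.3 uses the same terms for the MCEQ domain scores.

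**SAP 11.6.2.3.2 (MCEQ).** The model is fitted by REML, "using heterogeneous compound symmetry covariance structure", and the code carries this as "Random subject(sequence) / subject=subject type=csh". There is no REPEATED statement and no random product effect. If the model does not converge, the fallback order is `arh`, then `vc`, then `un`.

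**SAP 11.6.3.** The Cmax and AUC(0-last) sensitivity analysis in both groups runs "should there be 20% or more missing PK parameter values" and uses the "same mixed effects ANOVA model described in Section 11.6.2.3.2". The same analysis is done for tmax "in both Group-1 and Group-2 PK populations, supporting with THS 2.2 effect estimates on" tmax, there to adjust for period, sequence and subject. SAP 11.6.2.1.1 also points to 11.6.3 for a mixed-model check of AUC(0-∞), the partial AUC and half-life under the same 20% condition.

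**SAP 11.6.2.2.1 (CO and COHb), for contrast.** The RANDOM statement is plain, and `type=csh` sits on the REPEATED time-point effect, with the stated aim of letting variances differ between time points.

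**SAP section 9** lists changes from the protocol analysis. It does not mention a heterogeneous structure for the MCEQ or PK mixed model.

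**The concern.** Heterogeneous compound symmetry describes several correlated effects within a subject, each with its own variance. The MCEQ model has one random effect per subject and no time dimension. The structure and its fallback list match those of the CO/COHb model, but the reason given there does not carry over and no other is offered.

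At stake are the intervals for the MCEQ product differences and the supportive PK intervals. The primary GLM uses only subjects evaluable on both products, so for Cmax and AUC(0-last) this model is the planned check on all available data. It should not overstate precision in the missing-data setting that triggers it.

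**Working it through.** **Inputs from the documents.** 44 subjects in Group-1 and 18 in Group-2; within-subject CV for Cmax 36%; 10% dropout; 20% trigger. The documents give no between-subject variance, so that is assumed and varied. They also give no interval width for the mixed model.

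**The plan's own figures.** The SD of a log-scale paired difference is √(2·ln(1 + 0.36²)) = 0.4937.
- Group-1: the probability that the 95% half-width is at most ln 1.2 is 0.897 with 39 completers and 0.921 with 40. 39/0.9 = 43.3, rounded up to 44.
- Group-2: power for a ratio of 1.55 is 0.912 with 16 completers. 16/0.9 = 17.8, rounded up to 18.

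Both sample sizes reproduce.

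**What the code implies.** Under standard SAS nesting, `subject=subject` gives each subject a G block with one row per level of subject(sequence). Subject i's design matrix Z_i has a single non-zero column, its own. Hence Z_i G Z_i′ = σ_i² × (2×2 matrix of ones), whatever the correlation ρ. A numerical check with ρ = −0.02, 0, 0.5 and 0.9 gave the same matrix each time. So:
- Group-1: 44 variances + ρ (unidentified) + residual = 46 parameters for 2 × 44 = 88 observations.
- Group-2: 18 + 1 + 1 = 20 parameters for 36 observations.
- `arh` has the same defect. `un` in Group-1 would have 44 × 45/2 + 1 = 991 parameters. `vc` has 2.

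**Why the interval narrows.** With complete data the product estimate does not change. Subjects with small deviations have σ_i² estimated at zero, and those deviations are then counted as residual. At equal between- and within-subject variance the residual variance averages about 0.77 of its true value; √0.77 = 0.88, about 12% too narrow.

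**Size in Group-1.** REML simulation, 240 runs per cell, one variance per subject against one common variance, same containment degrees of freedom. The entry is relative interval width, followed by 95% CI coverage (per-subject v common variance).

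| Between/within variance ratio (assumed) | Complete data | 10% of values missing | 20% of values missing |
|---|---|---|---|
| 0.25 | 0.860; 88.3% v 93.8% | 0.834 | 0.799; 90.4% v 95.4% |
| 1 | 0.883; 92.9% v 96.3% | 0.847 | 0.801; 85.8% v 95.0% |
| 2 | 0.898; 94.6% v 95.8% | 0.860 | 0.809; 86.3% v 95.8% |
| 4 | 0.914; 92.5% v 95.4% | 0.876 | 0.819; 91.7% v 95.0% |
| 9 | 0.931; 92.5% v 95.0% | 0.897 | 0.840; 89.2% v 95.4% |

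The simulation error of a coverage figure is about √(0.95 × 0.05/240) = 1.4 points, so the widths are firmer than the coverages. Beyond the trigger the loss grows: 21-23% at 25% missing and 25-26% at 30% (ratios 1 and 4).

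**Size in Group-2.** At equal variances (150 runs) the relative width is 0.873 with complete data and 0.792 with 20% missing. A shorter run at ratio 2 gave 0.891 and 0.795. With CV 36% and an assumed between-subject log SD of 0.45, the ratio is 0.45²/ln(1.1296) = 0.2025/0.1219 = 1.66. With 40% of subjects lacking Period 2 (20% of values), the loss is then 22% in Group-2 and 19% in Group-1. Together this gives about 11-13% with complete data and 20-22% with 20% missing in Group-2.

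**The case against.** Several points stand and limit the finding.

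- **Reach.** Success depends on how precisely Cmax and AUC(0-last) are estimated, so a reader might infer that this line endangers the trial's success criterion. It does not. SAP 11.6.1 computes those intervals with PROC GLM and subject(sequence) fixed. Group-2 Cmax and AUC(0-last) use the same GLM, and the tmax test is a Wilcoxon signed-rank test.
- **MCEQ.** This is a descriptive secondary objective with no hypothesis. SAP 11.6.3 adds a percentile bootstrap that resamples subjects and does not rely on the model's standard error. For PK, a bootstrap table is listed, but the text of 11.6.3 describes the technique only for the two questionnaires.
- **Certainty.** With ρ unidentified and many variances at zero, `csh` may fail to converge. The ladder does reach the protocol's model, `vc`, but only after `arh`. Unlike 11.6.2.2.1, section 11.6.2.3.2 does not say that convergence problems will be reported. If the block is read as 1x1, there is no narrowing at all.
- **Likelihood of the larger figures.** If 10% of subjects lose Period 2, only 5% of values are missing, well below the trigger. The other route is the exclusion of subjects whose T0 concentration exceeds 5% of Cmax. If that removes whole subjects, complete pairs remain and the complete-data figure applies; a check with 20% of subjects removed gave 11%. If it is applied by period, the larger figures apply.
- **Prose.** The SAP text never assigns the structure to the random-effect matrix. Unequal variances for the two products would be a legitimate model, but the code does not fit it.

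None of this makes the statement correct.

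**Conclusion.** The point holds, as a should-fix. The covariance statement has no valid role on a single random subject effect and departs from protocol 12.5.3.

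If the `csh` or `arh` fit is accepted, product 95% intervals are too narrow by roughly 7-14% (complete data) to 16-20% (20% of values missing) in Group-1, and by about 11-13% to 20-22% in Group-2. These figures rest on SAS nesting rules that the documents do not state, on REML simulation outside SAS, on assumed between-subject variances and on the missing-data pattern. No single percentage should be read as a fixed property of the plan, and the narrowing is conditional.

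The analyses affected are the MCEQ differences, the triggered Cmax and AUC(0-last) sensitivity analysis, the tmax model, and the mixed-model check in 11.6.2.1.1 if triggered. The primary intervals, the success criterion and the Group-2 hypothesis tests stand.

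**What to change.** - In SAP 11.6.2.3.2, replace the RANDOM statement with `random subject(sequence);`, which has one variance, as in protocol 12.5.3.
- Remove heterogeneous compound symmetry from the prose and delete the `csh`/`arh`/`un` ladder for this model.
- Apply the same correction wherever 11.6.3 and 11.6.2.1.1 refer to it.

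Two additions are optional: `ddfm=kr`, and product-specific variances through a REPEATED statement on product if those are wanted.

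The cost is one line of code and the matching text. In Group-1, intervals would be wider than under the `csh` fit by about 8% (1/0.93 = 1.08) to 25% (1/0.80 = 1.25), over the range from complete data to 20% missing. No new data are needed and the primary analysis does not change.

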### 11.6.3 Supportive/Sensitivity Analysis

To support the interpretation of the PK analysis, the values of nicotine concentration greater than BLOQ before  $T_0$  will be listed together with any PK parameters excluded from the analysis. Listing will be presented by PK parameter impact, sequence, period and study date.

To better understand the impact of the higher than expected  $T_0$  values, an analysis of the PK parameters will be performed as described above, however the data for subjects with

their  $T_0$  value  $>5\%$  of their  $C_{max}$  value will be excluded from the analysis. Sensitivity analysis will be conducted on the  $C_{max}$  and  $AUC_{(0-last)}$  endpoints for the Group-1 and Group-2 PK populations should there be 20% or more missing PK parameter values. This analysis is conducted on all the available PK parameters and subjects will be excluded from the analysis if the nicotine concentration  $T_0$  value is  $>5\%$  of their  $C_{max}$  value. The analysis will be conducted in the natural log scale using the same mixed effects ANOVA model described in Section 11.6.2.3.2 “Modified Cigarette Evaluation Questionnaire”. Point and 95% interval estimates of the ratios will be back-transformed by exponentiation and tabulated.

The same sensitivity analysis for  $C_{max}$  and  $AUC_{(0-last)}$  endpoints will be conducted on  $t_{max}$ , in both Group-1 and Group-2 PK populations, supporting with THS 2.2 effect estimates on  $t_{max}$  adjusted for period, sequence, and subject within sequence.

In case any time information is imputed for the computation of PK parameters as described in Section 11.1.5 “Handling of Dropouts or Missing Data (including outside the limits of quantification)” in any PK population, the median  $t_{max}$  for THS 2.2 will be calculated following the imputation of missing time data by 0 sec and 30 sec. If the difference between the two median  $t_{max}$  is larger than 5%, a supportive analysis will be conducted by repeating the analyses described in Section 11.6.1 “Primary Analyses” and 11.6.2 “Secondary Analyses” on the  $t_{max}$ ,  $AUC_{(0-last)}$ , and  $AUC_{(0-t)}$  endpoints estimated by means of the imputation of missing time by 0 sec.

To evaluate the sensitivity to the distributional assumptions for the QSU-brief (see Section 11.6.2.3.1 “Urge-to-Smoke Questionnaire of Smoking Urges Brief”) and MCEQ (see Section 11.6.2.3.2 “Modified Cigarette Evaluation Questionnaire”) questionnaire scores, point and 95% interval estimates will also be assessed by means of the percentile bootstrap technique, using 2000 bootstrap samples which preserve the number of subjects per sequence. The data will be presented in the below outputs:

TFL number	Title
TABLES	
15.2.4.3.1	Supportive Analysis of Pharmacokinetic Parameters of Nicotine Excluding Subjects with $T_0$ Value $>5\%$ of Their $C_{max}$ Value – PK Population
15.2.4.3.2	Analysis of Pharmacokinetic Parameters of Nicotine by Bootstrapping Techniques – PK Population
15.2.4.4	Analysis of Pharmacokinetic Parameters of Nicotine by Zero Sec Imputation – PK Population
15.2.4.13	Analysis of QSU-brief Questionnaire Factors and Total Score by Bootstrapping Techniques – PK Population
15.2.4.16	Analysis of MCEQ Subscales by Bootstrapping Techniques – PK Population

## 11.6.4 Safety Evaluation

Safety variables monitored in this study include: AEs; vital signs (systolic and diastolic blood pressure, pulse rate, respiratory rate); spirometry; ECG data; concomitant medication, clinical chemistry, hematology, urine analysis safety panel, BMI, physical examination, respiratory symptoms (cough assessment).

The primary analysis of Safety parameters will be conducted on the Safety population as described in Section 11.1.3 “Descriptive Statistics”.

### 11.6.4.1 Safety Reporting

An exposure emergent AE is defined as an AE that occurs after first product use or that is present prior to first product use and becomes more severe after first product use. All other AEs will not be summarized but provided in listings only.

All AEs occurring from the signing of informed consent will be recorded electronically. The AE listings will include all AEs captured in the database at any time during the study (including those from subjects who were not in the safety population). All AEs occurred after the product test of THS 2.2 Menthol or NNS will be included in the summary tables. During the screening period prior to the first THS 2.2 Menthol or NNS product use, only study procedure related AEs will be included in the listings.

AEs reported from subjects that have a first product use, but were not randomized will be summarized in a separate sequence: “Exposed but not randomized”. The remainder of safety endpoints assessed in enrolled subjects that have a first product use, but were not randomized will be summarized in a separate sequence: “Enrolled but not randomized”.

Partial dates will not be imputed, but assumptions will be made as follows to assign to exposure-emergent or not:

Date information	Assign as
Partial date, e.g., --May2012, or ----2011. If month/year is the same as, or later than the month and/or year of Screening.	Exposure-emergent
Partial date, e.g., --May2012, or ----2011. If month and/or year is earlier than the month and/or year of Screening.	Not exposure-emergent

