8.2.2 Period of Collection

From the signature of the ICF onwards until EOS, all AEs (includes SAEs) will be collected by the study site staff as described below.

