**Table 1 Definition of Randomization Groups and Sequences**

Group	Allocation Ratio	Sequence	Sample Size
Group-1 = THS 2.2 Menthol vs. mCC	2:2	1. THS 2.2 Menthol then mCC 2. mCC then THS 2.2 Menthol	22 22
Group-2 = THS 2.2 Menthol vs. NNS	1:1	3. THS 2.2 Menthol then NNS 4. NNS then THS 2.2 Menthol	9 9

A Screening Visit will be conducted within 4 weeks prior to Admission to the investigational site (Day -29 to Day -2). A demonstration of the THS 2.2 Menthol product and the NNS will also be done by the site staff during the screening visit. Subjects will be admitted to the clinic on Day -1 (Admission). On Day -1, as the last procedure of the eligibility assessments on that day, all subjects will undergo a product test prior to enrolment, first THS 2.2 Menthol (using up to three Menthol Tobacco Sticks) and subsequently the NNS (1 spray of 0.5 mg per nostril as per label). In female subjects, the urine pregnancy test must be negative before the product test is performed with either THS 2.2 Menthol or NNS. After all inclusion and exclusion criteria have been met, only subjects willing and ready to use both the THS 2.2 Menthol and NNS products can be enrolled. Screening procedures do not necessarily have to be conducted on the same day.

Subjects are enrolled on Day -1, but not randomized until the Day 0 washout, therefore it is possible to have enrolled subjects who do not get randomized.

[figure not shown]
Subjects will be discharged from the investigational site in the morning of Day 4 after all safety examinations of the Day of Discharge have been conducted. After Discharge,

subjects will enter into a 7-day safety follow-up starting to capture spontaneously reported new AEs/SAEs and for active follow-up of ongoing AEs/SAEs. Any AE will in general be followed up until resolved, stabilized i.e., no worsening of the event, or until a plausible explanation for the event has been found.

The confinement consists of 2 periods (Period 1, Period 2) with each period consisting of at least 24-hour nicotine wash-out (nicotine abstinence) and 1 day of single product use.

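### The partial-date rule for exposure-emergent adverse events is anchored on Screening instead of first product use, so an event dated to a month before the product test is summarised as exposure-emergent

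*SAP*

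**What the plan says.** SAP 11.6.4.1 (Safety Reporting) gives the definition: "An exposure emergent AE is defined as an AE that occurs after first product use". The definition goes on to include an event already present before first use that becomes more severe afterwards. For everything else, "All other AEs will not be summarized but provided in listings only".

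First product use is fixed in SAP 6.1: "On Day -1, as the last procedure of the eligibility assessments on that day, all subjects will undergo a product test prior to enrolment". Screening lies between Day -29 and Day -2 (SAP 6.1, Protocol 4.1).

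The partial-date table in SAP 11.6.4.1 has two rows. A partial date is exposure-emergent "If month/year is the same as, or later than the month and/or year of Screening", and not exposure-emergent "If month and/or year is earlier than the month and/or year of Screening". Neither row mentions first product use, and neither says which date of the event is meant. Onset is the natural reading.

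On collection, SAP 11.6.4.1 states: "All AEs occurring from the signing of informed consent will be recorded electronically". Protocol 8.2.2 agrees: "From the signature of the ICF onwards until EOS, all AEs (includes SAEs) will be collected". Consent is given at the Screening Visit (Protocol 1.3.1).

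**The concern.** The definition and the rule that puts it into practice use different reference points. The same two-row wording appears in SAP 11.3.5 (medical history against concomitant disease) and SAP 11.6.4.5.1 (prior against concomitant medication). There Screening is the right anchor, because those categories are defined by Screening. Exposure-emergence is not. The wording may have been carried over without changing the anchor, but that is an inference. SAP section 9 lists no deliberate change, and no other part of the SAP corrects the rule.

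At stake is which events enter the adverse-event summaries. Protocol 12.6.5 makes adverse events the primary safety assessment, and Table 15.2.6.1 is both a safety-reporting output and a topline output (SAP 12.2 and 12.3). A pre-exposure event that belongs in the listings only would be counted in those summaries. Before first product use, only procedure-related events are to be reported (Protocol 8.2.2.1, SAP 11.6.4.1), so the events at risk are mainly of that kind.

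**Working it through.** The plan states no figure for this rule. The check is a comparison of the rule with the definition, followed by a calendar count.

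**Step 1: the window.** Screening is on Day -29 to Day -2 and the product test on Day -1, so the gap is 1 to 28 days. This agrees with the study duration in Protocol 4.3: 28 + 6 + 7 = 41 days at most and 1 + 6 + 7 = 14 days at least.

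**Step 2: what the rule does in the screening period.** Collection starts at consent, at Screening. The month of a new event's onset therefore cannot be earlier than the Screening month, and the rule classes every partly dated new event from the screening period as exposure-emergent.

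**Step 3: an example.** Screening is on 20 May and the product test on 10 June, an allowed gap of 21 days. An event is dated May, day unknown. May is not earlier than the Screening month, so the rule says exposure-emergent. May is earlier than June, so the event began before any product was used.

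**Step 4: which assignments are wrong.** If the known month is the month of the product test, the date cannot settle the order, and exposure-emergent is the usual cautious default. If the known month is after that, exposure-emergent is right. Only a known month before the product-test month gives a wrong class.

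**Step 5: how often that happens.** Assume that admission dates are spread evenly over a 365-day year, that gaps are uniform over 1 to G days, and that each combination of gap and onset day (from Screening to the day before Admission) has equal weight. The mean month length is L = 365/12 = 30.42 days. No month is shorter than 28 days, so an onset j days before the product test (j up to 28) falls in an earlier month for 12j of 365 admission dates, a share of j/L.

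- Share of screening-period onsets in an earlier month: the sum of j over all combinations is G(G+1)(G+2)/6, and the number of combinations is G(G+1)/2. The share is (G+2)/(3L) = (G+2)/91.25.
- Share of Screening and product-test pairs in different months: (G+1)/(2L) = (G+1)/60.83.

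| Longest gap G | Onsets in an earlier month | Pairs in different months |
|---|---|---|
| 28 days | 30/91.25 = 32.9% | 29/60.83 = 47.7% |
| 14 days | 16/91.25 = 17.5% | 15/60.83 = 24.7% |
| 7 days | 9/91.25 = 9.9% | 8/60.83 = 13.2% |

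A full enumeration of a calendar year gives the same percentages.

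**Step 6: after correction.** With first product use as the anchor, the shares in the middle column change class, apart from events that worsened after first use. The remainder (67.1%, 82.5% and 90.1%) share the product-test month and stay exposure-emergent by default.

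**The case against.** The strongest reply is that this will hardly ever matter. Protocol 8.2.1 asks for start and stop dates and times for each event, and Protocol 11.2.1 has missing data queried. Procedure-related screening events can usually be dated from the visit at which the procedure was done. The error also errs on the cautious side, much as SAP 11.6.4.2 counts a missing intensity as severe. Being classed as exposure-emergent does not make an event product-related: relation to product and relation to study procedure are tabulated separately (Tables 15.2.6.3 and 15.2.6.6). All of this stands, and it limits the size of the point. It does not reconcile the table with the definition. Where the known month precedes the product test, there is no ambiguity for a cautious default to resolve.

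A reader might infer more than the documents support:

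- *That every partly dated event is misclassified, or that the whole screening period of up to 28 days is.* The rule does class all partly dated new events as exposure-emergent, but those that start after the product test are rightly so, and those in the same month cannot be resolved from the date. On the uniform assumption, Screening and product test share a month in about 52% of pairs (100 - 47.7), and then nothing changes.
- *That the row for earlier dates is a second error because almost no new event can meet it.* It is redundant, and harmless.
- *That changing the anchor alone is enough.* A bare rule that an earlier month is not exposure-emergent would override the worsening part of the SAP's own definition. An event with onset in May that worsened after a June product test would be lost, which is under-counting. Protocol 7.4 and 8.2.1 require worsening to be recorded, but do not say that it becomes a separate record with its own date.

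**Conclusion.** The rule is wrong as written, within narrow limits. A partly dated event whose known month or year is at or after Screening but before that of the product test is summarised as exposure-emergent, contrary to the definition in the same section. Such events make up about 33% of partly dated screening-period events for gaps uniform over 1 to 28 days, 17.5% for gaps of at most 14 days and 9.9% for at most 7 days.

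These shares rest on the assumed uniform spread of dates, gaps and onsets, on reading the partial date as the onset date, and on a known month. They also leave aside later worsening. A year-only date is misclassified only when Screening and the product test fall in different calendar years. The documents give no count of partial dates; the absolute number of affected events is probably very small. The direction is over-counting, and neither the pharmacokinetic endpoints nor the success criterion is affected. This is a minor correction worth making.

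**What to change.** In both rows of the partial-date table in SAP 11.6.4.1, state that the date is the onset date and replace Screening by first product use (product test, Day -1). The rows then read in substance:

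- Month/year the same as or later than that of first product use, including a year-only date in the same year: exposure-emergent.
- Month/year earlier than that of first product use: not exposure-emergent, unless the event became more severe after first product use, in which case it stays exposure-emergent under the existing definition.

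The tables in SAP 11.3.5 and 11.6.4.5.1 need no change of anchor.

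The cost is a short edit and a small change to the derivation code. No new data are needed: product-test details are already to be listed (SAP 11.5), and the worsening condition already applies to fully dated events. If the SAP can no longer be amended before database lock, the change can be described in the study report, as SAP section 3 provides. With the same-month default and the worsening exception kept, the change of anchor drops no event that could meet the definition.
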